## 6.5. Booster Vaccination

All ongoing participants in the study who have received primary vaccination with the Ad26.COV2.S vaccine, or an mRNA vaccine or another authorized COVID-19 vaccine including protein, inactivated, and adenovector based vaccines and who have subsequently remained in the study will be offered to receive a 1-dose booster vaccination with Ad26.COV2.S at the  $5 \times 10^{10}$  vp dose level. Participants who have only received one dose of a two dose primary immunization regimen are also eligible to receive the booster vaccination with Ad26.COV2.S in this study. Participants in the study who have already received an additional COVID-19 vaccination after the primary regimen outside the study with any vaccine as described above will also be eligible for the Ad26.COV2.S booster in this study. Booster vaccination should occur preferably 6 months but at least 3 months after the last COVID-19 vaccination, but no later than the expiry date of the Ad26.COV2.S vials available at your site. Participants are free to choose when to receive the booster vaccination within the window of the booster vaccination visit, to receive booster vaccination outside the study, or not to receive booster vaccination. Participants who choose to receive a booster vaccination with the Ad26.COV2.S vaccine (if recommended and available) or another authorized COVID-19 vaccine outside the study or choose not to receive a booster vaccination will not be withdrawn from the study and will be encouraged to remain in the study.

Participants may be offered the single booster dose of Ad26.COV2.S vaccine under the following special conditions:

- Participants, who had met study discontinuation criteria under previous amendments, will be offered a single booster dose of Ad26.COV2.S vaccine at the discretion of the investigator, except the following participants (who are not eligible to receive the Ad26.COV2.S vaccine);
  - withdrew consent from the study or,
  - received any COVID-19-related experimental medication (including any experimental vaccines other than the study vaccine) or,

previously experienced TTS or heparin-induced thrombocytopenia (HIT) or, previously experienced capillary leak syndrome or, are planning to receive another COVID-19 vaccine within the 3 months after the booster vaccination.

- Participants who are pregnant may receive booster vaccination with Ad26.COV2.S, if allowed by local regulations and if the investigator considers that the potential benefits outweigh the potential risks to the mother and fetus.
- Participants who use systemic corticosteroids (chronic or recurrent use) or received antineoplastic and immunomodulating agents or radiotherapy may receive booster vaccination with Ad26.COV2.S if allowed by local regulations and after being made aware that the safety and efficacy data in patients using/receiving these medications/treatments is limited.
- Participants who have become infected with SARS-CoV-2 during the study may receive booster vaccination with Ad26.COV2.S vaccine, even if they received steroid treatment, convalescent plasma, or monoclonal antibody treatment, after they have recovered from the acute illness and at least 1 month has passed. Such participants should be made aware that the safety and efficacy data on vaccinating a previously infected individual is limited.
- Vaccination should be deferred in case of any other illness, until the person has recovered from the acute illness (see Section [5.5](#)).

Investigators will be encouraged to follow health authority guidelines on prioritization of immunization when feasible. Investigators are encouraged to consider current local public health guidance for determining the scheduling priority of participants when feasible, eg, participants with comorbidities and/or of specific age groups can be scheduled prior to participants without comorbidities if this is in line with local guidance. Based on operational considerations, the investigators at their discretion may prioritize those participants who had their priming regimen at a more distant time prior to the booster vaccination.

All participants will be counselled to continue practicing other public health/preventative measures that were introduced at the start of this pandemic (eg, social distancing, face masks, frequent hand washing), in compliance with local and national guidelines. Participants who receive booster vaccination with Ad26.COV2.S will continue to follow the Schedule of Activities in Section [1.3](#).

As of Protocol Amendment 7, no further booster doses will be administered, except if there was a medical reason that prevented a participant to receive the Ad26COV2.S vaccine prior to acceptance of amendment 7 or if there is a non-availability of other vaccines to the participant. The investigator should inform participants on the availability of other COVID-19 vaccines.

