#### 1.3.1. Non-immunogenicity or Non-Booster Subset Participants (As of Amendment 7)

Phase	Study Period	Long-term Follow-up Phone Calls		Early Exit Phone Call
Visit number	6 a	7 (previously numbered as Visit 10)	8 (previously numbered as Visit 11)	Exit b
Visit Timing	Primary Vac +52 w	Booster +24 w	Booster +52 w	
Visit Day/Week	Year 1 (Week 52)	Month 18 (24 weeks after Year 1 Visit)	Year 2 (52 weeks after Year 1 Visit)	
Visit Window	Preferably 6 months, but at least 3 months after last COVID-19 vaccination*	±28 d	±28 d b	
Informed consent for Amendment 7 c	● #			
MAAE recording g		Continuous		●
(SAE recording h		Continuous		●
Passive follow up of COVID 19 i		Continuous		●
Concomitant therapies j		Continuous		

Phase	Study Period	Long-term Follow-up Phone Calls		Early Exit Phone Call
Visit number	6 a	7 (previously numbered as Visit 10)	8 (previously numbered as Visit 11)	Exit b
Visit Timing	Primary Vac +52 w	Booster +24 w	Booster +52 w	
Visit Day/Week	Year 1 (Week 52)	Month 18 (24 weeks after Year 1 Visit)	Year 2 (52 weeks after Year 1 Visit)	
Visit Window	Preferably 6 months, but at least 3 months after last COVID-19 vaccination*	±28 d	±28 d b	
Activities below are only applicable to those that will receive a booster vaccination under special circumstances m		No further booster vaccination is to be given as of Protocol Amendment 7**		
Body temperature d	●#,+ d			
Urine pregnancy test e	●#,+ e			
Pre vaccination symptoms f	●#,+ f			
Vaccination	●+ f			
Clinical laboratory blood sample (whole blood), mL k,l	●#,+7 k,l			
Approx. blood draw range per visit, mL	7 ml			

\* pre vaccination

\* ie, preferably within window of 100 to +170 days around Year 1, but no later than the expiry date of the Ad26.COV2.S vials available at your site.

\*\* Except if there is a medical reason that prevents a participant to receive the Ad26COV2.S vaccine prior to acceptance of Amendment 7 or if there is a non availability of other vaccines to the participant, but no later than the expiry date of the Ad26.COV2.S vials available at your site

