a applicable for participants who receive(d) a single dose of Ad26.COV2.S booster vaccination at the Year 1/Booster Visit under the conditions delineated in Section 6.5 (more details in Section 8.10) and for participants who receive(d) a booster vaccination outside of the study. Participants who choose to receive a booster vaccination outside of the study are encouraged to schedule their Year 1/Booster Visit prior to their booster vaccination, if feasible, and come in for the Year 1 + 28 Days visit within the specified visit window, if feasible, or as close as possible to the visit window. As of protocol amendment 7, some participants may still receive a booster, for those subjects, the follow up should be a least 6 months post vaccination, but the last visit can be shorter than 1 year post vaccination.

- If allowed by local regulations, study visit 6 may take place at the participant's home or other location in the event of ongoing SARS-CoV-2 transmission in the area of the participant. If possible and allowed per local regulation, visits can be performed by a phone call or a telemedicine contact. Except for the vaccination visit, assessments scheduled for the other visits may also be performed by a trained health care professional (HCP), if allowed per local regulations.
- For those participants who are unable to continue participation in the study up to Visit 8, but for whom consent is not withdrawn, an early exit visit will be conducted as soon as possible. Participants who wish to withdraw consent from participation in the study will be offered an optional visit for safety follow-up.
- Reconsenting may take place at the Year 1/Booster Visit or, if Visit 6 already occurred, at an unscheduled visit and may be performed on-site or by phone as per local regulations.
- Body temperature will be measured preferably via the oral route, or in accordance with the local standard of care.

- e. For participants of childbearing potential only. Participants who are pregnant may receive booster vaccination with Ad26.COV2.S, if allowed by local regulations and if the investigator considers that the potential benefits outweigh the potential risks to the mother and fetus (see Section 6.5).

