## **5. STUDY POPULATION**

Screening for eligible participants will be performed within  $\leq 28$  days before randomization and administration of the study vaccine, or on the day of the vaccination. Refer to Section [5.4](#) for conditions under which the repeat of any screening procedures are allowed.

The inclusion and exclusion criteria for enrolling participants in this study are described below. Some inclusion and exclusion criteria only apply to a particular stage (1a, 1b, 2a, and/or 2b), as indicated below. See Section [4.1](#) for more details about enrollment in the different stages. If there is a question about these criteria, the investigator must consult with the appropriate sponsor representative and resolve any issues before enrolling a participant in the study. Waivers are not allowed.

Once enrolled, all participants who received placebo during the double-blind phase will be eligible to receive vaccination with Ad26.COV2.S at the Month 6/Unblinding Visit if they agree and consent to receive the active vaccine and meet the criteria described in Section [6.4](#).

As of Amendment 6, all ongoing participants who have previously received any COVID-19 vaccination(s) (as primary regimen or additional dose) with the Ad26.COV2.S vaccine, and/or an mRNA vaccine or another COVID-19 vaccine authorized for primary vaccination including protein, inactivated, and adenovector based vaccines will be eligible to receive a 1-dose booster vaccination with Ad26.COV2.S at the  $5 \times 10^{10}$  vp dose level at the Year 1/Booster Visit if they agree and consent to receive the active vaccine and meet the criteria described in Section [6.5](#).

For a discussion of the statistical considerations of participant selection, refer to Section [9.2](#).

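### Section 6.5 attaches the booster bars for prior TTS/HIT and capillary leak syndrome only to the bullet on earlier discontinuation, so read literally they do not limit the general booster offer

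*Protocol*

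**What the plan says.** Section 6.5 opens with the general offer: "All ongoing participants in the study who have received primary vaccination with the Ad26.COV2.S vaccine, or an mRNA vaccine", or another authorized vaccine, may have one booster dose. The limits in that paragraph are the interval since the last COVID-19 vaccination and the vial expiry date.

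A list of special conditions follows. Its first bullet is about participants who had met study discontinuation criteria under earlier amendments. They "will be offered a single booster dose of Ad26.COV2.S vaccine at the discretion of the investigator, except the following participants", and a parenthesis describes the excepted people as those "who are not eligible to receive the Ad26.COV2.S vaccine". The exceptions are withdrawn consent, receipt of COVID-19-related experimental medication, and then: "previously experienced TTS or heparin-induced thrombocytopenia (HIT) or, previously experienced capillary leak syndrome or, are planning to receive another COVID-19 vaccine within" 3 months after the booster. The remaining bullets (pregnancy, immunosuppression, past infection, other illness) do not repeat these items.

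Other sections rely on 6.5 to decide who may be boosted. Section 5 makes participants eligible at the "Year 1/Booster Visit if they agree and consent to receive the active vaccine and meet the criteria described in Section" 6.5. The Amendment 7 schedule in Section 1.3.1 speaks of "booster vaccination at the Year 1/Booster Visit under the conditions delineated in Section 6.5", adding that more details are in Section 8.10.

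The rule is still live. Section 1.3.1 notes: "As of protocol amendment 7, some participants may still receive a booster". Sections 4.1 and 6.5 give two routes: an earlier medical reason for not being vaccinated, or no access to another vaccine.

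**The concern.** The bars on TTS/HIT and capillary leak syndrome look as though they are meant for anyone about to receive the vaccine, yet their sentence has a narrower subject. One site could take the list as a general bar. Another could take it as an exception to a concession made only for people who had earlier met a discontinuation criterion. The two would then treat the same medical history differently.

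What is at stake is participant safety. Section 2.3.1 calls TTS an important identified risk of Ad26.COV2.S and says that the condition can be fatal. A bar of that kind should not have to be inferred from a parenthesis.

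**Working it through.** No arithmetic applies. The protocol gives no rate of TTS, HIT or capillary leak syndrome and no number of boosters given under the Amendment 7 exceptions. The check is to set the texts side by side.

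**Step 1: scope of the exception list.** The general offer covers all ongoing, primed participants. The list belongs to a sentence whose subject is those who had met discontinuation criteria. The literal gap is everyone in the first group who is not in the second.

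| Item in the 6.5 list | Effect if limited to the discontinuation bullet |
|---|---|
| Withdrew consent | None; such a person is not an ongoing participant |
| COVID-19-related experimental medication | Compatible with the other text (step 4) |
| Prior TTS or HIT | No bar in 6.5 for other participants |
| Prior capillary leak syndrome | No bar in 6.5 for other participants |
| Another COVID-19 vaccine planned within 3 months | No bar in 6.5 for others, but little remaining effect (step 5) |

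**Step 2: do the entry or deferral criteria close the gap?** Section 5.2 names none of TTS, HIT or capillary leak syndrome. The nearest criteria are the investigator's opinion on underlying conditions (criterion 9) and contraindications to injections and blood draws, such as bleeding disorders (criterion 10). Section 5.5 lists temporary contraindications only: acute illness, fever, and illness that could interfere with early safety assessment.

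**Step 3: do the pre-booster procedures close it?** Section 1.3.1 introduces a short block of procedures: "Activities below are only applicable to those that will receive a booster vaccination under special circumstances". These are temperature, a pregnancy test, pre-vaccination symptoms and a blood sample. The footnote on symptoms asks for a check of acute illness or raised temperature. The blood count includes platelets, but a current count does not establish a past history.

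**Step 4: is the narrow reading one a careful site could reach?** Two features of the text support it.

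- In Section 6.4, which uses the same sentence for the cross-over dose, the bar on having received another authorized vaccine stands in the first bullet and again among the exceptions in the discontinuation bullet. If that second list covered everyone, the repetition would be unnecessary.
- The 6.5 list bars anyone given COVID-19-related experimental medication. Yet a later bullet of 6.5 allows boosting after infection treated with convalescent plasma or monoclonal antibodies, and Section 6.10 allows investigational COVID-19 drugs after diagnosis. Where such treatment was experimental, a general reading of the whole list would conflict with that bullet.

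**Step 5: what is left under Amendment 7?** The planned-vaccine bar is nearly moot on the non-availability route, because a person with no access to another vaccine is unlikely to be planning one. It could matter on the medical-reason route. The bars on TTS/HIT and capillary leak syndrome could matter on either. The period is short: boosters end at vaccine expiry, and Section 5.5 allows a delayed booster no later than 15 May 2022.

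**The case against.** The strongest reply is that the parenthesis states ineligibility without qualification. It would be odd for prior TTS to bar someone who once met a discontinuation criterion but not someone who never did. Section 2.3.1 also describes the risk plainly and refers sites to the Investigator's Brochure. This stands as evidence of intent: the problem is one of drafting, and nothing in the protocol shows that any site has read the sentence narrowly.

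The second reply is that the answer may lie elsewhere. Section 2.3.3 says that vaccination is discontinued for the reasons in Section 7, and Section 1.3.1 points to 8.10. Neither 7.1 nor 8.10 was available to this review. Section 7.1 may bar these people outright, or may make TTS a discontinuation criterion and so bring them inside the bullet. This limits the claim to the wording of 6.5.

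A reader might infer more than the text supports in three ways:

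- **That the protocol has no general bar.** This cannot be concluded without Sections 7.1 and 8.10.
- **That participants primed outside the study with another adenovector vaccine are a group at particular risk.** Section 6.5 does admit them, but nothing in the text reviewed links those vaccines to TTS, HIT or capillary leak syndrome.
- **That the bullet reopens dosing after anaphylaxis.** Its exceptions do not name anaphylaxis, but it gives the investigator discretion and no duty to dose. Sections 5.2 and 2.3.1 exclude people with such a history from the study, and anaphylaxis after a study dose is a matter for Section 7.1.

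**Conclusion.** The point holds as a defect in the wording of Section 6.5. The bars for prior TTS/HIT and prior capillary leak syndrome, and with little remaining effect the bar for a planned other vaccine, belong grammatically to one bullet and do not limit the general offer. The conclusion rests on 6.5 being the section that others name for booster eligibility, and on Sections 5.2, 5.5 and 1.3.1 supplying no substitute bar.

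The magnitude is low: few participants, no derivable count, a short period, and a probable intent that most investigators would recognize. Correction is still worthwhile because the rule governs dosing, the risk can be fatal and the change is nearly free. Alpha, power, endpoints and the efficacy conclusions are not affected.

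**What to change.** Move the bars for prior TTS/HIT, prior capillary leak syndrome and a planned other COVID-19 vaccine within 3 months out of the discontinuation bullet. Put them in a stand-alone sentence in Section 6.5 that applies to every Ad26.COV2.S booster, including those given under the Amendment 7 exceptions.

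Do not make the whole list general as it stands. Leave the experimental-medication item under the discontinuation bullet, or reconcile it with the past-infection bullet of 6.5 and with Section 6.10. Check the new sentence against Sections 7.1 and 8.10 so that the three places agree.

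Using the same wording in Section 6.4 is optional, since Section 2.1 describes the cross-over offer in the past tense.

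The cost is a wording change and a memo to sites, with no new procedures or data. The downside is that a handful of boosters might not be given.

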## **6.6. Study Vaccine Compliance**

Study vaccines will be administered intramuscularly by a study vaccine administrator – a trained and qualified study nurse, medical doctor, or otherwise qualified HCP. The date and time of study vaccine administration and the location used will be recorded in the eCRF.

## 6.7. Dose Modification

Dose modification is not applicable in this study.

## 6.8. Continued Access to Study Vaccine After the End of the Study

Prior to EUA, conditional licensure, or approval in any country, participants who opt for enrollment in an Expanded Access Program or a Phase 3b study (eg, Sisonke/TOGETHER in South Africa) may be unblinded upon their request and will be encouraged to continue in study VAC31518COV3001. Study investigators should query participants to elicit and document such participation in other studies in the VAC31518COV3001 study record.

Following EUA, conditional licensure, or approval in any country and approval of protocol Amendment 4 by the local Health Authority and IEC/IRB, participants who initially received placebo will be offered a single dose of Ad26.COV2.S study vaccine at no cost, as described in Section 6.4.

With approval of Amendment 6 by the local Health Authority and IEC/IRB, ongoing participants who have previously received any COVID-19 vaccination(s) (as primary regimen or additional dose) with the Ad26.COV2.S vaccine, and/or an mRNA vaccine or another COVID-19 vaccine authorized for primary vaccination including protein, inactivated, and adenovector based vaccines will be offered a single booster dose of Ad26.COV2.S study vaccine at no cost, as described in Section 6.5.

At the time when another COVID-19 vaccine is determined to be efficacious and authorized/licensed for use, some participants may become eligible to receive such vaccine, depending on country-specific conditions (eg registration status, local recommendations/regulations, vaccine availability or the specific target group for vaccination). The investigator will discuss with the participants the available information and options to allow the participant to make an informed choice as to whether they qualify to receive the authorized/licensed vaccine and whether they should request individual unblinding to take up the offer of an authorized/licensed COVID-19 vaccine. Safety evaluations will be identical for all participants, including participants that are unblinded to obtain an authorized/licensed COVID-19 vaccine and who remain in the study. Access to Ad26.COV2.S vaccine for participants already unblinded will be under the conditions delineated in Section 6.4. All data will be analyzed from the point of unblinding for safety, efficacy, and immunogenicity, as described in the SAP.

## 6.9. Treatment of Overdose

For this study, any dose of Ad26.COV2.S greater than the assigned dose will be considered an overdose. The sponsor does not recommend specific treatment for an overdose.

In the event of a known overdose, the investigator should:

- Contact the medical monitor immediately.

- Closely monitor the participant for AE/SAE/MAAE (ie, the participant will remain at the study site for at least 1 hour and will be closely monitored for allergic or other reactions by study staff. Follow-up telephone calls 12 hours and 24 hours post-dose will be made).
- Document the quantity of the excess dose in the source document.
- Report as a special reporting situation.

## 6.10. Prestudy and Concomitant Therapy

Prestudy therapies are only to be recorded for participants with relevant comorbidities and participants aged  $\geq 60$  years. For these participants, all prestudy therapies (excluding vitamins, herbal supplements; non-pharmacologic therapies such as electrical stimulation, acupuncture, special diets, and exercise regimens) administered up to 30 days before the vaccination must be recorded at screening.

For all participants, concomitant therapies associated with an SAE or suspected AESI meeting the criteria outlined in Section 10.4.1 and Section 8.3.7, respectively, will be collected and recorded in the eCRF from the moment of vaccination (or from the time of local approval of protocol Amendment 5 for suspected AESIs) through the end of the study. Concomitant therapies associated with MAAEs will be collected and recorded in the eCRF from the moment of vaccination until 6 months after (double-blind or open-label) Ad26.COV2.S. Concomitant therapies associated with MAAEs leading to study discontinuation will be recorded in the eCRF during the entire study.

For all participants, concomitant therapies associated with COVID-19 will be captured in the electronic eCRF for the duration of the study. This will still be applicable after implementation of Protocol Amendment 7. Hence, under protocol amendment 7, concomitant medication in case of COVID-19 (S)AEs and COVID-19 MAAEs need to be recorded, as well any confirmatory laboratory result, if available (eg positive COVID-19 PCR results, positive nasal swab). The assay methodology should be mentioned.

For participants in the Safety Subset, concomitant therapies associated with unsolicited AEs will be collected and recorded in the eCRF from the time of vaccination through 28 days after double-blind vaccination. Concomitant therapies associated with solicited AEs will be collected by the participants and recorded in the eCRF from the time of vaccination through 7 days after double-blind vaccination.

Antipyretics are recommended post-vaccination for symptom relief as needed. Prophylactic antipyretic use is not encouraged; however, in some instances, it could be considered for participants with special circumstances and/or comorbidities.

Participants may not have received an investigational drug (including investigational drugs for prophylaxis of COVID-19) within 30 days or used an invasive investigational medical device within 30 days or received investigational Ig or monoclonal antibodies within 3 months, or received convalescent serum for COVID-19 treatment within 4 months or received an investigational vaccine (including investigational Adenoviral-vectored vaccines) within 6 months

before the planned administration of the study vaccine. During the study, the use of investigational vaccines other than the study vaccine is not allowed, and the use of investigational drugs is only allowed if medically indicated. Treatment with investigational COVID-19 drugs after diagnosis of a COVID-19 case is allowed during the follow-up period and needs to be recorded in the COVID-19 episode description.
